#### **4.4 Aim 2: Adapted TranS-C versus Standard TranS-C on Fit to CMHC Context**

MLM will be used to account for multiple observations nested within providers. TranS-C treatment condition (Adapted versus Standard TranS-C) will be evaluated as a predictor of fit, operationalized as provider ratings of acceptability, feasibility, and appropriateness. The level 1 equation will include dummy-coded time indicators as the predictor (0 = pre-treatment, 1 = post-treatment). The level 2 equation will include dummy-coded treatment condition (0 = Standard TranS-C, 1 = Adapted TranS-C), treatment by time interaction terms, and dummy-coded counties (0 = Alameda, 1 = Contra Costa, 2 = Kings, 3 = Monterey, 4 = Placer, 5 = Santa Cruz, 6 = Solano, 7 = Santa Clara, 8 = Santa Barbara, and 9 = Lake) as predictors. The treatment effects of interest will be significant treatment by time interactions at the 5% level on the primary outcome of acceptability and the secondary outcomes of feasibility and appropriateness, all modeled as continuous variables. Significant treatment by time interactions indicate that change in perceptions of fit is significantly different comparing Adapted to Standard TranS-C. Significant interactions will be interpreted using planned contrasts (i.e., treatment effects on change from pre-treatment to post-treatment) and graphs.

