### Methods:

TranS-C will be implemented in at least ten counties in California, United States (N = 96 providers; N = 576 clients) via facilitation. CMHC sites are cluster-randomized by county to Adapted TranS-C or Standard TranS-C. Then, within each county, patients are randomized to immediate TranS-C or usual care followed by delayed treatment with TranS-C (UC-DT). Aim 1 will compare TranS-C (combined Adapted and Standard) with UC-DT on improvements in sleep and circadian problems, functional impairment, and psychiatric symptoms. Sleep and circadian problems will also be tested as a mediator between treatment condition (combined TranS-C versus UC-DT) and functional impairment/psychiatric symptoms. Aim 2 will evaluate whether Adapted TranS-C is superior to Standard TranS-C with respect to provider perceptions of fit. Aim 3 will evaluate whether the relation between TranS-C treatment condition (Adapted versus Standard) and patient outcomes is mediated by better provider perceptions of fit in the Adapted condition. Exploratory analyses will: (1) compare Adapted versus Standard TranS-C on patient perceptions of credibility/improvement and select PhenX Toolkit outcomes; and (2) evaluate possible moderators.

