**Table 1. SPIRIT Depiction of Timing and Measures Collected for Implementation Phase**

[figure not shown]
	Screening	Post-Training	Pre-Treatment	Mid-Treatment	Post-Treatment	6-Months Post-Treatment
Patient						
Sociodemographics			X		X	X
Eligibility Items	X					
PROMIS-SD P	X		X	X	X	X
PROMIS-SRI			X	X	X	X
DSM-5 Cross-Cutting			X		X	X
SDS			X		X	X
Sleep Health Composite			X	X	X	X
PHENX Toolkit			X		X	X
CEQ					X	
Provider						
Sociodemographics		X				
Occupation		X				
Acceptability P		X		X	X	
Appropriateness		X		X	X	
Feasibility		X		X	X	
Number of Sessions					X	

*Note.* Allocation to Adapted or Standard TranS-C occurs at the county level and prior to enrollment of any participants in that county (i.e., patients or providers). Enrollment of patients and allocation to immediate TranS-C or delayed TranS-C (UC-DT) occur after the screening and before the pre-treatment assessment. Enrollment of providers after the training. P = Primary Outcome. PROMIS-SD = PROMIS-Sleep Disturbance; note: PROMIS-SD is only assessed during the pre-treatment assessment if done more than one month after the screening to minimize burden for patients. PROMIS-SRI = PROMIS-Sleep Related Impairment. SDS = Sheehan Disability Scale. CEQ = Credibility/Expectancy Questionnaire

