Adapted TranS-C will be superior to Standard TranS-C with respect to the primary provider outcome of acceptability and the secondary provider outcomes of appropriateness and feasibility. The third aim is to evaluate whether better fit mediates the relation between TranS-C treatment condition and patient outcome. We hypothesize that relative to Standard TranS-C, Adapted TranS-C will be associated with greater reductions in the primary and secondary patient outcomes indirectly through higher provider ratings of acceptability, appropriateness, and feasibility. Exploratory analyses will: (1) compare Adapted and Standard TranS-C on patient perceptions of credibility/improvement and select PhenX Toolkit outcomes; and (2) determine whether treatment effects are moderated by risk factors including age, sex, and sleep and circadian and psychiatric symptoms at baseline [50, 51].

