#### 3.4.1 Standard TranS-C

Standard TranS-C is delivered by CMHC providers across eight 50-minute, weekly sessions [40]. It is comprised of 4 cross-cutting modules featured in every session, 4 core modules, and 7 optional modules that are used based on clinical presentation, treatment goals, and provider case conceptualization. The *cross-cutting modules* are case formulation, sleep and circadian education, motivational enhancement, and goal setting. *Core module 1* targets irregular sleep-wake times, difficulty winding-down, and difficulty waking-up. *Core module 2* aims to reduce daytime impairment. *Core module 3* focuses on unhelpful beliefs about sleep. *Core module 4* aims to promote maintenance of changes made during treatment. *Optional module 1* addresses poor sleep efficiency via stimulus control [64] and sleep restriction [65]. *Optional module 2* helps patients reduce time in bed. *Optional module 3* addresses delayed or advanced phase problems (e.g., going to sleep later than desired or waking up earlier than desired). *Optional module 4* helps patients manage worries about sleep. *Optional Module 5* promotes compliance with Continuous Positive Airways Pressure (CPAP) for patients with sleep apnea. *Optional Module 6* helps patients negotiate sleep in complicated environments (e.g., noise from bed/roommates, traffic noise, streetlight entering the bedroom). *Optional Module 7* is for patients who experience nightmares. Training for the Standard TranS-C condition consists of a 1-day workshop (i.e., 6-8 hours) or two, 3-hour training blocks.

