#### 3.4.2 Adapted TranS-C

Adapted TranS-C is delivered by CMHC staff across four, 20-minute, weekly sessions. Treatment consists of the same four *cross-cutting and core modules* as in Standard TranS-C, but the core modules are split up into five, rather than four, modules. *Core module 1* targets irregular sleep-wake times. *Core module 2* targets difficulty winding down. *Core module 3* targets difficulty waking up. *Core module 4* aims to reduce daytime impairment. *Core module 5* promotes maintenance of change. The one *optional module* focuses on reducing sleep-related worry and can be integrated with the core modules, based on clinical presentation, treatment goals, and provider case conceptualization. Training for the Adapted TranS-C condition consists of four, 1-hour workshops or two, 2-hour workshops, based on CMHC preferences.

There have been calls for rigorous approaches to treatment adaptation [66, 67]. In response, we grounded the process for adapting TranS-C in theory, data, and stakeholder input. As the overarching guide for the adaptation process, the Replicating Effective Programs (REP) framework [47] was used. Phase 1 of REP (Pre-Condition) was completed prior to the present protocol. First, as discussed above, we established that

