#### 3.6.1 Providers

Provider assessments are completed after TranS-C training, at mid-treatment, and at post-treatment. See Figure 4 for provider timeline.

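### Aim 2's time 0 is a post-training rating, and the planned model tests only change from it: no Adapted-Standard difference in fit can be estimated at any rating

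*Combined protocol and SAP*

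**What the plan says.** The Abstract says "Aim 2 will evaluate whether Adapted TranS-C is superior to Standard TranS-C with respect to provider perceptions of fit". Section 2 predicts that "Adapted TranS-C will be superior to Standard TranS-C with respect to the primary provider outcome of acceptability", with appropriateness and feasibility secondary. Neither sentence names a time point or mentions change. Section 3.8 powers Aim 2 on d = 0.80 between the two versions, also without a time point.

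Section 4.4 describes a two-time model: "The level 1 equation will include dummy-coded time indicators as the predictor (0 = pre-treatment, 1 = post-treatment". It names the condition by time interaction as the effect of interest, and its follow-up contrasts concern change only. Section 4.1 likewise describes the Adapted-Standard comparisons as change from pre-treatment, and it enters counties as dummy variables in every model.

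On timing, section 3.6.1 says "Provider assessments are completed after TranS-C training, at mid-treatment, and at post-treatment". The note to Table 1 adds "Allocation to Adapted or Standard TranS-C occurs at the county level and prior to enrollment of any participants in that county" and "Enrollment of providers after the training". Training differs by arm. Section 3.4.1: "Training for the Standard TranS-C condition consists of a 1-day workshop", or two 3-hour blocks. Section 3.4.2: "Training for the Adapted TranS-C condition consists of four, 1-hour workshops or two, 2-hour workshops".

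**The concern.** A difference in change isolates a treatment effect when the first measurement precedes exposure. Here the first rating comes after providers have been trained in their county's version and have learned its length and content. Any effect of the version on perceived fit that arises in training is already in the time 0 rating, and the interaction subtracts it.

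Acceptability is the primary provider outcome. If Adapted is preferred from training onward and stays equally preferred, the interaction is zero and the trial would report no effect although the stated hypothesis is true. If Adapted starts lower and catches up, the interaction is positive without Adapted ending ahead. The planned model offers no between-arm difference that would tell these cases apart.

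**Working it through.** **1. Which rating is time 0?** Table 1 and section 3.6.1 list three provider ratings: post-training, mid-treatment and post-treatment. Time 1 is post-treatment, so time 0 can only be post-training. The documents do not say this outright, but no other reading fits.

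**2. The plan's own figure.** Inputs from section 3.8: d = 0.80, two-sided alpha 0.05, ICC 0.01, J = 8 clusters, n = 10 providers each.
- Inflation factor: 1 + 9 × 0.01 = 1.09.
- SE = sqrt(4 × (ICC + (1 − ICC)/n)/J) = sqrt(4 × 0.109/8) = 0.2335 SD.
- Non-centrality = 0.80/0.2335 = 3.43.
- Non-central t with 8 − 2 = 6 df gives 81.3%. At 9 per cluster it gives 77.6%.

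The stated 10 per cluster for over 80% power is therefore reproduced.

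**3. What the interaction estimates.** Let D0 and D1 be Adapted minus Standard at post-training and post-treatment. The interaction is D1 − D0, which equals D1 only if D0 = 0. With D1 = 0.80 and D0 = 0.80f, it is 0.80(1 − f).

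**4. Whether the model can give D0 or D1.** The fixed effects in section 4.4 are intercept, time, condition, condition by time and county dummies. I read the county list as a set of indicators, as section 4.1 says. County is the randomised unit, so condition is a sum of county indicators. With 8 counties there are 11 columns and rank 10; with 10 counties, 13 columns and rank 12. The interaction is estimable. Condition, and condition plus interaction, are not. Without the dummies the four-term model has full rank.

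**5. Power of the planned interaction.** Assumed, not in the documents: f; the within-provider correlation rho; equal SDs at both ratings; the 1.09 factor kept for change; df bracketed from county level (J − 2) to provider level (78). Non-centrality = 0.80(1 − f)/(sqrt(2(1 − rho)) × SE). Section 3.3.1 lists ten counties, so the same 80 analysed providers are also taken as 10 × 8: SE = sqrt(4 × 0.13375/10) = 0.2313.

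| f (rho = 0.5) | 8 × 10, 6 to 78 df | 10 × 8, 8 to 78 df |
|---|---|---|
| 0 | 81-92% | 86-93% |
| 0.25 | 58-72% | 62-73% |
| 0.5 | 30-40% | 33-40% |
| 1 | 5% | 5% |

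At 8 × 10, rho = 0.3 gives 68-82% at f = 0 and 23-30% at f = 0.5; rho = 0.7 gives 96-99% and 46-59%.

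**6. The other direction.** If f < 0, the interaction exceeds the final gap. If Adapted starts 0.40 SD lower and ends level, D1 = 0 but the interaction is 0 − (−0.40) = 0.40, the same size as at f = 0.5, so it is significant 30-40% of the time at rho = 0.5 and 8 × 10.

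**7. Precision of a post-treatment contrast with county as cluster.** At ICC 0.01: 8 × 10 gives 81% power and a 95% half-width of 2.447 × 0.2335 = 0.57 SD; 10 × 8 gives 86% and 2.306 × 0.2313 = 0.53 SD. At an assumed ICC of 0.05, power is 70% and 77%.

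**The case against.** Sections 4.1 and 4.4 consistently describe change, and testing change is a legitimate choice. A post-training rating does precede treatment delivery, and Table 1 discloses its timing. All of this stands. The fault is that hypothesis and estimand are not reconciled and that time 0 is not described as following exposure.

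A reader might infer that the Abstract and section 2 promise superiority at post-treatment. They do not, since neither names a time point. A reader might also take section 3.8 as proof that a level difference was powered, because its figure reproduces as a comparison of arm means at one time. That does not settle it: at f = 0 and rho = 0.5 the interaction on 6 df also gives 81.3%, and section 3.8 uses the same between-arm wording for TranS-C versus UC-DT, which section 4.3 tests as treatment by time.

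The harm also rests on f and rho, which the documents do not give. Section 1 reports that staff saw dose and complexity as barriers to Standard TranS-C, which makes an early gap possible but does not establish one. Section 3.7 says providers are not told which version their county has. That makes explicit comparison less likely, though each provider still rates after training in one version.

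One could reply that condition is in the model, so condition plus interaction gives the post-treatment difference. The county dummies rule that out.

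**Conclusion.** The point holds in this form: time 0 follows exposure to the arm's training; the only planned test is the difference in change after it; the model as specified cannot yield an Adapted-Standard difference at any rating; and the documents do not reconcile the superiority hypothesis with that test. The timing is firm, and so is the rank result, given county as the randomised unit.

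The size is conditional. With no early gap the planned test answers the question, at 81-92% power (8 × 10) or 86-93% (10 × 8) for rho = 0.5. With a quarter of the gap present early, about 20 percentage points are lost. With half present, power is below half of its f = 0 value, and with all of it present the test rejects 5% of the time. A lower Adapted start works the opposite way. It would go too far to say that Aim 2 will fail, or that an early gap exists; the documents support neither. This should be fixed, because a primary outcome is affected and the data needed are already scheduled.

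**What to change.** 1. In section 4.4, relabel time 0 as post-training and state that it follows exposure to the arm's training.
2. State whether the Aim 2 hypothesis and the section 3.8 power concern the level of acceptability or change after training. Reconcile the Abstract, section 2 and section 3.8 with sections 4.1 and 4.4.
3. Keep the interaction as the confirmatory test in the Benjamini-Hochberg family of section 4.1. Beside it, pre-specify one supportive contrast: Adapted minus Standard acceptability at post-treatment. Report the post-training and mid-treatment differences descriptively. Estimate all of these from a model of the three ratings with county as the cluster (random effect or county-level analysis, small-sample df), without county dummies and without adjusting for the post-training rating. If the sponsor prefers the level contrast as confirmatory, it must enter that family. The small-sample df and a reported interval answer section 4.1's concern about few clusters.
4. Interpret the interaction together with the level differences. A null or reversed interaction alone is not evidence against superiority, and a positive one alone is not evidence for it if Adapted started lower.

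The cost is one added model and some wording, with no new data. The level contrast is imprecise (working, step 7) and keeps county and provider-selection differences that change removes: counties are few and unstratified (section 3.7), and providers join by interest and after training (sections 3.2 and 3.3.2, Table 1). That is why it is supportive. Recruitment has ended (section 6) and some outcomes are shown to CMHC leadership (section 3.9), so the addition should be dated, registered as section 3 requires, and say whether arm-level provider results had been seen.

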#### **4.5 Aim 3: Fit as a Mediator of Treatment Condition and Patient Outcome**

Multilevel structural equation modeling will be used to test whether improved perceptions of fit (i.e., acceptability, appropriateness, and feasibility) mediate the relation between TranS-C treatment condition (i.e., Adapted versus Standard TranS-C) and change in the primary patient outcome of sleep disturbance and the secondary patient outcomes of sleep-related impairment, functional impairment, and psychiatric symptoms. Models will evaluate change in outcomes from pre-treatment to post-treatment and pre-treatment to 6FU.

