### 4.3 Aim 1: Effectiveness Outcomes of Standard or Adapted TranS-C versus UC-DT

Multilevel modeling (MLM) [100-102] will be used to account for multiple observations nested within

patient. The level 1 equation will include dummy-coded time indicators as the predictor (0 = pretreatment, 1 = post-treatment). The level 2 equation will include dummy-coded treatment condition (0 = UC-DT, 1 = Adapted or Standard TranS-C), treatment by time interaction terms, and dummy-coded counties (0 = Alameda, 1 = Contra Costa, 2 = Kings, 3 = Monterey, 4 = Placer, 5 = Santa Cruz, 6 = Solano, 7 = Santa Clara, 8 = Santa Barbara, and 9 = Lake) as predictors. The treatment effects of interest will be significant treatment by time interactions at the 5% level on the primary outcome of sleep disturbance and the secondary outcomes of sleep-related impairment, functional impairment, and psychiatric symptoms, all modeled as continuous variables. Significant treatment by time interactions indicate that change in patient outcomes is significantly different comparing Adapted or Standard TranS-C to UC-DT. Significant interactions will be interpreted using planned contrasts (i.e., treatment effects on change from pre-treatment to post-treatment) and graphs. Additionally, the indirect effects of TranS-C relative to UC-DT on functional impairment and psychiatric symptoms through improvements in sleep disturbance and sleep-related impairment will be tested using multilevel structural equation modeling [103].

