### **5 DISCUSSION**

This study aims to evaluate implementation and effectiveness outcomes of the Transdiagnostic Intervention for Sleep and Circadian Dysfunction (TranS-C) delivered to patients in community mental health centers (CMHCs) by CMHC providers. Findings will address several research priorities. First, TranS-C was designed to target a wide range of serious mental illness (SMI) diagnoses through addressing a wide range of sleep and circadian problems [35, 40]. As such, TranS-C has the potential to improve symptoms of patients with diverse and complex clinical presentations, which may help alleviate provider burden and optimize patient care [18, 19]. Second, providers play a pivotal role in the day-to-day delivery of mental health care. Thus, it is critical to assess their perceptions of implemented treatments. The present findings will advance our understanding of providers' perceptions of TranS-C's 'fit' – namely, acceptability, feasibility, and appropriateness – which is an important predictor of implementation outcomes (e.g., fidelity, reach, sustainability; [15-17]). Third, leaders in the implementation science have advocated for causal tests of implementation strategies [108]. Heeding this call, the present study tests whether adapting TranS-C to CMHCs improves 'fit' between the treatment and context, and if so, whether this improved fit is associated with better patient outcomes. Evaluating this implementation strategy (i.e., adapting treatments to fit contexts) may help other implementation scientists evaluate whether it is a worthwhile implementation strategy to pursue.

These potential contributions should be considered alongside the protocol's methodological limitations.

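### Section 4 specifies no total or direct Adapted-versus-Standard effect on the patient outcomes, so Aim 3 can be met by the indirect path through fit even if the net effect favours Standard

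*Combined protocol and SAP*

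**What the plan says.** Section 4.5 states the Aim 3 analysis: "Multilevel structural equation modeling will be used to test whether improved perceptions of fit (i.e., acceptability, appropriateness, and feasibility) mediate the relation" between version (Adapted or Standard) and change in sleep disturbance and three secondary patient outcomes, to post-treatment and to 6FU. Section 2 words the hypothesis as an indirect one: "Adapted TranS-C will be associated with greater reductions in the primary and secondary patient outcomes indirectly through higher provider ratings" of fit.

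The other analysis sections do not supply the overall comparison of versions on these outcomes:

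- Section 4.3 (Aim 1) pools the versions, with "dummy-coded treatment condition (0 = UC-DT, 1 = Adapted or Standard TranS-C". Section 4.8 (moderators) uses the same pooled coding.
- Section 4.4 (Aim 2) compares the versions on provider ratings only.
- Section 4.6 reruns Aims 1 to 3 in subsets.
- Section 4.7 compares the versions on PhenX outcomes and credibility, as exploratory analyses.
- Section 4.1 and the Discussion say that comparisons of Adapted with Standard cover change to post-treatment and to 6FU. They give time windows, but no model, contrast or reading rule.

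The Abstract nevertheless asks whether adapting improves patient outcomes as well as provider ratings, and section 3.8 claims over 80% power for d = 0.50 between the versions under Aims 1 and 3.

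**The concern.** A contrast is asked about and powered but never specified. In its place stands a mediation hypothesis that the path from version to fit to outcome can satisfy by itself.

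That matters here because the two paths may oppose each other. Standard is planned as "eight 50-minute, weekly sessions" and Adapted as "four, 20-minute, weekly sessions". Section 1 reports that centre staff named dose and complexity as barriers, and that Adapted was developed in response. So the feature meant to raise provider ratings could also reduce direct benefit to patients. If it did, the total effect could favour Standard while Aim 3 was reported as supported, and the plan has no rule for reading that result.

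**Working it through.** **1. Planned contact.** Sections 3.4.1 and 3.4.2: 8 × 50 = 400 minutes for Standard and 4 × 20 = 80 for Adapted. Ratio 80/400 = 0.20.

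**2. The plan's power figure.** Inputs from section 3.8: J = 8 clusters, 30 immediate-treatment patients per cluster (240/8), d = 0.50, two-sided alpha 0.05. The ICC of 0.01 is given in the Aim 2 text and is assumed here for patient outcomes.

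SE = sqrt(4 × [ICC + (1 − ICC)/n] / J) = sqrt(4 × [0.01 + 0.99/30] / 8) = 0.147 SD.

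With a noncentral t on J − 2 = 6 df, power is 81%, which agrees with the stated figure of over 80%. So section 3.8 describes a plain difference between versions, and section 4 has no test to match it.

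**3. Precision of the total effect.** Half-width = t(0.975, 6 df) × SE.

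| ICC | SE | 95% CI half-width | Power at d = 0.50 |
|---|---|---|---|
| 0.01 | 0.147 | 2.447 × 0.147 = 0.36 SD | 81% |
| 0.05 (assumed) | 0.202 | 2.447 × 0.202 = 0.49 SD | 54.5% |

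**4. How often the two results could diverge.** Positive values favour Adapted. Indirect = a × b, and total = a × b − direct cost. Only a = 0.80 is the plan's (expected effect on acceptability, section 3.8). The slope b (SD of outcome per SD of fit), the direct cost and a provider ICC of 0.05 are assumptions. The simulation used 80 providers with 3 patients each (240/80, immediate arms only) or 6 (480/80, if delayed patients also enter, which the plan does not say). It had 4,000 runs and a joint-significance test of a and b at 5%. Cells give the share of trials with a significant favourable indirect effect and a total point estimate favouring Standard, for 3 / 6 patients per provider. Monte Carlo error is at most about 1.5 points.

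| b | cost 0.10 | cost 0.40 | cost 0.50 |
|---|---|---|---|
| 0.05 | 7% / 10% | 10% / 15% | 11% / 15% |
| 0.10 | 16% / 25% | 27% / 45% | 29% / 45% |
| 0.20 | 25% / 26% | 72% / 89% | 76% / 90% |

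The true total is negative in every cell except b = 0.20 with cost 0.10 (0.16 − 0.10 = +0.06). The event requires only a negative total estimate, not a significant one. This simulation has no county level, so it illustrates the logic and does not reproduce the planned model.

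**5. Identification.** Section 4.1 enters counties as dummy variables in all models, and version is constant within county. For a change score in ten counties, an intercept, nine dummies and version make 11 columns of rank 10, so a version main effect is not identified. In the repeated-measures form, adding time and version-by-time gives 13 columns of rank 12. Dropping version-by-time lowers the rank to 11, so that term is estimable. But without a county-by-time term, its standard error ignores between-county variation in change.

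**The case against.** The strongest reply is that a mediation SEM normally estimates the direct path too, and that total equals direct plus indirect. Sections 3.8 and 4.1 and the Discussion together show that a comparison of versions was intended, and nothing says the direct or total effect would be withheld. This stands: the gap is an unwritten specification, and a reader should not infer that the sponsor will look only at the indirect path. It does not close the gap, because no section commits to reporting those effects or says how to read paths of opposite sign.

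A reader might also infer that the Discussion makes the indirect effect the test of whether adapting is worthwhile. It does not. It asks "whether this improved fit is associated with better patient outcomes", and says only that evaluating the strategy may help others to judge its worth. The section 2 hypothesis is openly indirect, so reporting a significant indirect effect as indirect would be accurate. Offsetting paths are a legitimate mediation finding.

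Finally, the simulated shares follow from inputs that the documents do not give. That also stands, and it is why only the wide range is reported.

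**Conclusion.** The point holds as a gap in specification. The plan asks about and powers an Adapted-versus-Standard difference on patient outcomes, but it defines no total or direct effect for them. Its Aim 3 hypothesis can therefore be met while the net effect favours Standard.

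The size cannot be fixed from the documents. The range of roughly 7% to 90% rests on the plan's a = 0.80 together with assumed values of b, direct cost and provider ICC, so no single figure should be taken as the expected frequency. A reader might infer from the one-fifth contact time that Adapted patients will do worse. The documents do not support that: they show that opposing paths are possible and say nothing about which is larger.

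**What to change.** In section 4.5:

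1. Prespecify the total Adapted-minus-Standard effect on change in PROMIS-SD and the secondary patient outcomes, at post-treatment and at 6FU.
2. Report total, direct and indirect effects together, each with a 95% CI.
3. For this contrast, replace the county dummies with a county-level error term, or use a county-level analysis with small-sample df. The version effect is then identified and its error reflects randomisation by county.
4. State that a favourable indirect effect alone will not be described as showing that Adapted improves patient outcomes, and that paths of opposite sign will be reported as offsetting.

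A rule that allows the Aim 3 claim only when the total effect does not favour Standard is not recommended. It would have to say whether it means the estimate or the interval. On the estimate, it blocks about half of trials in which the true total is zero. On an interval of ±0.36 SD, it would seldom block modest harm.

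No new data are needed, but this is more than a wording change, because the county term in the model must change. The price is a more cautious Aim 3 conclusion and a fairly wide interval for the total effect.
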